3.10 STUDY MANAGEMENT

3.10.1 Sponsor

Pierre Fabre Médicament will serve as the Sponsor of this study. It is the responsibility of Pierre Fabre to ensure proper oversight of the contract research organization (CRO) conducting protocol development, implementation and monitoring of the study and compliance with all applicable regulatory guidelines and laws.

3.10.2 CRO responsible for the management of the study

Clinact will serve as the CRO of this study. It is the responsibility of Clinact to develop the statistical analysis plan and clinical study reports, manage recruitment, training, monitoring, management of sites, EDC and data management and analysis under guidance, input, review, and approval of Pierre Fabre.

3.10.3 Scientific Committee (SC)

A scientific committee will be established before the study initiation. Three experts, including 2 clinicians and 1 methodologist, will serve as members on this committee over the study period. The role of this committee will be (i) to validate the study documents (i.e. protocol & CRF), (ii) to validate the survey results and site selection, (iii) to validate study results and interpretation, and (iv) to be involved in the communication and publication plan.

Three main meetings are planned during the study and remote meetings will be planned during the study conduct. More information regarding the roles and responsibilities of the SC, the timing of meetings, methods of providing information, frequency and format of meetings, will be detailed in the Charter.

3.11 LIMITATIONS OF THE RESEARCH METHODS

3.11.1 Selection bias

Selection bias may arise if the study sample differs substantively from the underlying target population of patients with BRAF^{V600E} mutant mCRC. To minimize selection bias, the eligibility criteria are selected to be as broad as possible, and all patients meeting the selection criteria will be enrolled consecutively. Furthermore, to the extent possible, patients will be recruited from a diverse pool of clinical sites. Finally, where applicable, minimal de-identified information, including the

reason for non-participation, will be collected for patients who are not enrolled in the study to assess whether there may have any systematic differences between participant and non-participants.

3.11.2 Information bias

Inaccurate assessment of study variables may occur in observational research, especially in medical chart review studies. To minimize information bias, clear definitions of the variables of interest will be provided to ensure accurate assessment of the desired data elements, and detailed eCRF completion guidelines will be provided to the site staff to ensure accurate entry of data into the EDC. The eCRFs will include programmable edits to identify missing, out of range, illogical, or potentially erroneous data. All eCRFs will be completed by trained site personnel. In addition, routine monitoring will be conducted and source data verification may be performed to ensure the quality of the data collected.

3.11.3 Follow-up bias

Follow-up bias may occur when differences exist between study participants and patients lost to follow-up or discontinued. The study will be operationalized in such a way to minimize patient loss to follow-up through careful procedures that are minimally burdensome for the patients and the sites.

4 PROTECTION OF HUMAN SUBJECTS AND LOCAL REGULATORY ASPECTS

4.1 ETHICS

To ensure the quality and integrity of research, this study will be conducted under the guidelines of good pharmacoepidemiology practices (GPPs) issued by the International Society for Pharmacoepidemiology (ISPE), the Declaration of Helsinki and its amendments, the EU General Data Protection Regulation (GDPR) and any applicable national guidelines.

The investigator will be responsible for ensuring that the observational study will be performed in accordance with the protocol, and applicable regulatory and country-specific requirements.

4.2 INDEPENDENT ETHICS COMMITTEE OR INSTITUTIONAL REVIEW BOARD (IEC/IRB)

Consistent with local regulations and prior to enrollment of patients at a given site, the study protocol will be submitted together with its associated documents (e.g., ICF) to the responsible institutional review board (IRB)/independent ethics committee (IEC) for its review. Before implementation of any substantial changes to the protocol, protocol amendments will also be submitted to the relevant IRB/IEC in a manner consistent with local regulations. Pertinent safety information will be submitted to the relevant IECs during the course of the study in accordance with local regulations and requirements.

This study will be undertaken only after the IRB/IEC have given full approval of the final protocol, the ICF and applicable recruiting materials, and the Sponsor had received a copy of this approval.

4.3 PATIENT INFORMATION

For the patients who are alive at the time of data collection, information of the patient about use of their health data in completely anonymized form will be ensured by either sending an information letter or, if required, presenting an ICF, which must be signed by the patient (or the patient's next of kin) before his or her participation in the study. The patient will also be informed that the local care team will keep a record of their data entry for a short period of time only and that it will not be possible to exercise their rights laid down in the GDPR (notably article 15-20) after anonymization by destruction of this record. For deceased patients, a waiver of informed consent/authorization will be requested from the relevant IRB/IEC, where applicable and in accordance with national regulations, for the collection of anonymized data.

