In each participating center, all eligible patients will be identified and assigned a random number. Data will be abstracted consecutively. If necessary applicable by local regulations, written informed consent from patient or next of kin (for patients alive at the time of data abstraction and for dead patients, if required by local regulations) will be obtained prior to data abstraction. If consent is needed and not provided, the reason will be noted in a screening log.

Data collection/data sources

The source of collected data will be all elements that can constitute a reliable source of patient-level information and that are available at the site. This includes data available in the patient medical charts (e.g., consultation notes, discharge summaries, laboratory test results, recorded prescription data and any other documentation of communication with other health care providers). The site investigator will be responsible for ensuring that all the required data is collected and entered into the eCRF.

The exposure of interest will be the first line SACT (monotherapy, doublet chemotherapy, or triplet chemotherapy with or without a targeted therapy [either VEGF inhibitor or EGFR inhibitor]) for the treatment of BRAF^{V600E} mutant mCRC.

The following key data items will be collected, where available:

- Patient demographic and clinical characteristics
 - Age, gender, weight, height, body mass index at mCRC diagnosis
 - Date of diagnosis of CRC and mCRC
 - Performance status using Eastern Cooperative Oncology Group score at mCRC diagnosis
 - Comorbidities at mCRC diagnosis
 - Tumor/node/metastasis stage (I, II, III, IV) at the time of initial diagnosis of CRC
 - Histology at the time of initial diagnosis of CRC: adenocarcinoma, other carcinoma

- Location of the primary tumor at the time of initial diagnosis of CRC: colon left-sided, colon right-sided, colon transverse, rectum, unknown
- Tests and diagnosis collected at mCRC diagnosis or during follow-up
 - Tumor Biomarker Assessments: BRAF on tumor sample or ctDNA (including date of ordering test and date of test result); RAS; MSI (microsatellite instability); MMR (mismatch repair)
 - Blood biomarker assessments: C-reactive protein; CEA; CA 19-9
- Biological parameters
 - Other selected routine laboratory tests at at mCRC diagnosis
- Metastasis
 - Location: Liver, lung, lymph nodes, bone, peritoneum, central nervous system, other locations, unknown
 - Number of metastatic sites

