3.2.2.2 Exclusion criteria

Patients will be excluded from the study if they fulfil any of the following criteria:

- Patients with another concomitant cancer at the time of diagnosis*
- Patients participating in interventional trials on investigational drugs at the time of initiation of first-line treatment

* Except for non-metastatic non-melanoma skin cancers, or in situ or benign neoplasms; a cancer will be considered concomitant if it occurs within 5 years of mCRC diagnosis.

For patients who fulfil the eligibility criteria, but do not participate in the study (non-consent, non-inclusion because of patient selection process), a screening log will be maintained (subject to local regulations) to record the reason for non-participation, gender, age at diagnosis (pre-defined categories), first line treatments received (if available) and survival status.

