3.2.3 Participants recruitment and follow-up

3.2.3.1 Participant selection process

In each participating center, all eligible patients' medical records will be identified. The following steps will be followed for patient selection:

- Participating sites (wherever feasible) will be asked to list exhaustively all eligible patients in an pseudonymized way
- The pseudonymized patient list will then be given a number of enrollment
- Medical records will be abstracted by the site staff until reaching the targeted number of patients per site or reaching the end of the list
- The patient will be informed of this data collection according to applicable regulations. If the patient has opposed to data collection, the reason will be noted and the next record from the enrollment list will be identified.

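### Where deceased patients enter under a consent waiver and living patients can decline, inclusion depends on the OS event, and the protocol plans no analysis to correct for it

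*Combined protocol and SAP*

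**What the plan says.** Living and deceased patients enter by different routes.

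- **Living patients.** Section 4.3 ensures their information by "either sending an information letter or, if required, presenting an ICF", and the form has to be signed before participation. Section 3.2.3.1 adds: "If the patient has opposed to data collection, the reason will be noted and the next record from the enrollment list will be identified". Abstraction continues as follows: "Medical records will be abstracted by the site staff until reaching the targeted number of patients per site or reaching the end of the list".
- **Deceased patients.** Section 4.3 states: "For deceased patients, a waiver of informed consent/authorization will be requested from the relevant IRB/IEC". The same sentence makes this conditional on the waiver being applicable and on national rules. The Synopsis (Patient selection process) also provides for written consent from the patient or next of kin, "for patients alive at the time of data abstraction and for dead patients, if required by local regulations".
- **Non-participants.** Where local rules permit, the screening log in section 3.2.2.2 records the reason, gender, age category, "first line treatments received (if available) and survival status". Section 3.11.1 gives the purpose of the information on patients not enrolled: "to assess whether there may have any systematic differences between participant and non-participants".
- **Analysis.** Section 3.8.3 plans Kaplan-Meier curves for OS and PFS, with the median and the 25th and 75th percentiles, and optional Cox models on baseline covariates. Sections 3.8.1 to 3.8.5 contain no weighting and no sensitivity analysis for selective participation. Section 3.8.1 defers details to a separate SAP, which is not in the file.

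**The concern.** Where the waiver is granted, a deceased patient cannot be lost through refusal or non-response, while a living one can. Selection then acts on vital status at abstraction, which is the OS event. Adjusting for baseline covariates cannot remove selection on the outcome. Taking the next record restores the number of patients but not the mix of living and dead.

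The patients lost are the long survivors, so the upper part of the OS distribution suffers most. PFS is affected less, because it is tied to vital status at abstraction only indirectly.

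The Study Rationale says the results are meant to put the single-arm ANCHOR trial into context and may support health technology assessment. An OS estimate that is too low for standard care would flatter a new regimen set beside it. This bias does not shrink as more patients are enrolled.

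**Working it through.** **The plan's own figure.** The only size calculation is the precision of a proportion (section 3.5, Table 5). With n = 300, 1.96·√(p(1−p)/300) gives ±2.47%, ±3.39% and ±4.53% at 5%, 10% and 20%, which matches. The documents give no precision for OS and no refusal rate.

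**Inputs from the documents.** Median OS m is 10 to 15 months (section 1). Treatment starts from January 2016 to December 2018, a window of 36 months (section 3.1). Observation ends on 31 January 2020, month 49 (section 3.2.3.2). Data entry starts in April 2020 and database lock is in November 2020 (Table 6), so abstraction is placed at T = 52 or T = 58 months.

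**Assumptions.** Entry is uniform and survival is exponential with λ = ln 2 / m. A share r of patients alive at abstraction is lost at random, and every deceased patient is kept.

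**Step 1: share alive at abstraction.** A = [e^(−λ(T−36)) − e^(−λT)] / (36λ). For m = 12.5 and T = 52, λ = 0.05545 and A = (0.4118 − 0.0559)/1.996 = 17.8%.

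**Step 2: median in the selected sample.** The observed curve is (S(t) − rA)/(1 − rA). Setting it to one half gives S(t) = (1 + rA)/2, so the median falls by m·log2(1 + rA). For m = 12.5, T = 52 and r = 30%: 12.5 × log2(1.0535) = 0.94 months.

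| m (months) | T | A | Shift, r = 10% | Shift, r = 30% |
|---|---|---|---|---|
| 10 | 52 | 12.1% | 0.17 | 0.51 |
| 10 | 58 | 8.0% | 0.11 | 0.34 |
| 12.5 | 52 | 17.8% | 0.32 | 0.94 |
| 12.5 | 58 | 12.8% | 0.23 | 0.68 |
| 15 | 52 | 23.3% | 0.50 | 1.46 |
| 15 | 58 | 17.6% | 0.38 | 1.12 |

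The formula ignores censoring, which starts 13 months after entry at the earliest. A simulation of 1,000,000 patients with the January 2020 cut-off agrees with these shifts to about 0.01 month.

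**Step 3: other summaries (simulation, r = 30%).** The 75th percentile is about 0.9 to 3.7 months too low, and 24-month OS about 1.6 to 4.5 points too low. With a heavier tail (Weibull, shape 0.8), the median is 0.2 to 0.7 months too low at r = 10% and 0.7 to 2.2 months too low at r = 30%.

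**Step 4: the sign can change.** If a share r of the dead is lost and all the living are kept, the median rises by −m·log2(1 − rA/(1 − r)). At r = 10% this is 0.1 months for m = 10, A = 8.0%, and 0.6 months for m = 15, A = 23.3%. With equal loss in both groups the bias is about zero.

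**Step 5: does weighting work?** Weighting living participants by 1/(1 − r) returned the simulated median to within 0.03 months of the truth at r = 30%. The date used for vital status matters. About 3% to 9% of patients die between the January 2020 cut-off and abstraction. If abstraction-date rates are applied to status at the cut-off, the weighted median is 0.2 to 0.9 months too high at r = 30%.

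**The case against.** A reader might infer that every deceased patient enters automatically, that OS is therefore biased downwards throughout the study, and that replacement makes it worse. The documents do not support this. The waiver is only requested and depends on national rules. The Synopsis foresees consent for deceased patients where required, and the inclusion criteria name next of kin. Step 4 shows that the sign can then reverse. Replacement adds no bias beyond the removal itself.

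The size is also open. Many patients may be covered by an information letter and non-opposition, for which a 30% loss is not evidenced. At 10%, the shift is small beside sampling error. With n = 300 and no censoring, the 95% half-width of the median is about 1.96·m/(ln 2·√300), or ±1.6 months at m = 10 and ±2.4 months at m = 15.

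OS is a secondary, descriptive endpoint. The primary objective is treatment patterns, no hypothesis is tested, and ANCHOR is described as assessing confirmed response rate. The log and the comparison in section 3.11.1 show that the authors had non-participation in mind, and the SAP may say more.

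All of this stands as a limit on direction, size and importance. It does not close the gap. Comparing participants with non-participants may reveal a difference in vital status, but it does not say what that difference does to the OS curve.

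**Conclusion.** The concern holds conditionally. Where a waiver applies to the dead and the living may decline, inclusion depends on the OS event, and OS is likely too low. Where deceased patients also need consent, the bias may vanish or reverse, so its sign can differ by country.

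On the stated assumptions, median OS is about 0.1 to 0.5 months too low at 10% loss of the living and 0.3 to 1.5 months too low at 30%, and more with a heavier-tailed curve. The loss rates are assumptions. The statement that no correction is planned applies to the protocol's analysis section only. This is a change that should be made, with medium confidence: it is cheap, and it will show the bias to be negligible if it is.

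**What to change.** In section 3.8.3:

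1. Report participation by vital status beside the OS and PFS results.
2. Pre-specify a sensitivity analysis of OS and PFS that weights each participant by the inverse of the participation rate in his or her vital-status stratum. Using each stratum's own rate corrects a bias in either direction. Keep the unweighted analysis as the main one.
3. Define vital status at one common date, namely when the record is selected for abstraction, and capture it as the same field in the eCRF and the log. Give patients of unknown status their own stratum.

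The cost is one added field and one weighted Kaplan-Meier analysis per endpoint. It should be settled before database lock, because section 3.7 has the sites' enrollment record destroyed at that point.

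There are limits. The analysis is possible only where local rules allow the log. It assumes that non-participants resemble participants of the same vital status. Weights may have to be pooled across countries: section 3.2.3.2 keeps centre and country out of the patient number and carries that anonymization into the analysis database, although section 3.8.1 plans analyses by country. The SAP should state which applies.

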4.4 PRIVACY OF PERSONAL DATA

Confidentiality of patient records will be maintained at all times. All study reports will contain aggregate data only and will not identify individual patients, physicians, hospital sites or even countries. Medical record abstraction will only be performed after receiving the approval from an IRB/IEC or equivalent, as applicable by national regulations. At no time during the study will the Sponsor receive patients' identifying information, except when it is required by regulations in case of reporting AEs.

In order to maintain patient confidentiality, each patient will be randomly assigned a unique patient identifier upon study enrollment which will guarantee anonymisation of the collected data from the moment of data entry. All parties will ensure protection of patient personal data and will not include patient names on any study forms, reports, publications or in any other disclosures, except where required by law. In accordance with local regulations in each of the countries, patients will be informed about data handling procedures and asked for their consent, if applicable by national regulations. Data protection and privacy regulations will be observed in capturing, forwarding, processing, and storing patient data.

4.4.1 Personal data protection

Pierre Fabre Medicament (PFM) as Sponsor of the study and data controller is responsible for the processing of personal data in accordance with the provisions of Regulation 2016/679/EU of the European Parliament and of the Council of 27 April 2016 on the protection of natural persons with regard to the processing of personal data and the free movement of such data (GDPR), the data collected being for research purposes in the field of health, the legal basis of the processing being the legitimate interest of the data controller.

5 MANAGEMENT AND REPORTING OF ADVERSE EVENTS/ADVERSE REACTIONS

5.1 TRAINING

Not applicable.

5.2 REPORTING OF ADVERSE EVENTS/ADVERSE DRUG REACTIONS

5.2.1 Definitions

Adverse event (AE); synonym: Adverse experience

Any untoward medical occurrence in a patient or clinical trial subject administered a medicinal product and which does not necessarily have a causal relationship with this treatment [Dir 2001/20/EC Art 2(m)].

An AE can, therefore, be any unfavorable and unintended sign (e.g., an abnormal laboratory finding), symptom or disease temporally associated with the use of a medicinal product, whether or not considered related to the medicinal product.

Adverse reaction; synonyms: ADR, suspected adverse (drug) reaction, adverse effect, undesirable effect

A response to a medicinal product which is noxious and unintended [DIR 2001/83/EC Art 1(11)].

Response in this context means that a causal relationship between a medicinal product and an AE is at least a reasonable possibility. An adverse reaction, in contrast to an adverse event, is characterized by the fact that a causal relationship between a medicinal product and an occurrence is suspected. For regulatory reporting purposes, if an event is spontaneously reported, even if the relationship is unknown or unstated by the healthcare professional or consumer as primary source, it meets the definition of an adverse reaction. Therefore, all spontaneous reports notified by healthcare professionals or consumers are considered suspected adverse reactions, since they convey the suspicions of the primary sources, unless the primary source specifically state that they believe the event to be unrelated or that a causal relationship can be excluded.

Adverse reactions may arise from use of the product within or outside the terms of the marketing authorization or from occupational exposure [DIR 2001/83/EC Art 101(1)]. Use outside the marketing authorization includes off label use, overdose, misuse, abuse and medication errors.

Serious adverse reaction

An adverse reaction which results in death, is life-threatening, requires in-patient hospitalization or prolongation of existing hospitalization, results in persistent or significant disability or incapacity, or is a congenital anomaly/birth defect is considered a serious adverse reaction [DIR 2001/83/EC Art 1(12)].

Life-threatening in this context refers to a reaction in which the patient was at risk of death at the time of the reaction; it does not refer to a reaction that hypothetically might have caused death if more severe (ICH-E2D Guideline).

Medical and scientific judgement should be exercised in deciding whether other situations should be considered serious reactions, such as important medical events that might not be immediately life-threatening or result in death or hospitalization but might jeopardize the patient or might require intervention to prevent one of the other outcomes listed above. Examples of such events are intensive treatment in an emergency room or at home for allergic bronchospasm, blood dyscrasias or convulsions that do not result in hospitalization or development of dependency or abuse (ICH-E2D Guideline).

Any suspected transmission via a medicinal product of an infectious agent is also considered a serious adverse reaction. Misuse of a medicinal product can occur from situations where the medicinal product is intentionally and inappropriately used not in accordance with the authorized product information.

Overdose

Administration of a quantity of a medicinal product given per administration or cumulatively which is above the maximum recommended dose according to the authorized product information. Clinical judgement should always be applied.

Abuse

Persistent or sporadic, intentional excessive use of medicinal products which is accompanied by harmful physical or psychological effects [DIR 2001/83/EC Art 1(16)].

Medication error

Are unintentional errors in the prescribing, dispensing or administration of a medicine while under the control of a healthcare professional, patient or consumer. They are the most common single preventable cause of AEs in medication practice.

Occupational exposure

For the purpose of reporting cases of suspected adverse reactions, an exposure to a medicinal product as a result of one's professional or non-professional occupation.

